If you are not able to supply all pertinent information with the initial submission, once the additional information is available **do not submit a new report**. Go to the original email that was received by STRC and others "reply to all" and entitle your email "**Amendment**" for (list date of event and patient ID) this will avoid duplications of the same event. List the additional information which you are reporting.

Acronyms and Definitions

STRC-Safety and Toxicity Review Committee

SAE-Serious Adverse Event

IRB-Institutional Review Board

WFBCCC-Comprehensive Cancer Center Wake Forest University

ORIS-Oncology Research Information System

NCI-National Cancer Institute

CPDM-Clinical Protocol and Data Management

Interventional Trials-Therapeutic Level 1 and Level 2 trials

Therapeutic Level 1-A cancer treatment protocol aimed at directly treating/curing the patient's cancer.

Therapeutic Level 2-A therapeutic protocol not cancer treatment involves clinical activity to treat symptoms, improve the patient's quality of life, or prevent cancer.

THE USE OF LIPOSOMAL BUPIVACAINE FOR PAIN CONTROL FOLLOWING MASTECTOMY AND IMMEDIATE IMPLANT BASED BREAST RECONSTRUCTION

Wake Forest Baptist Comprehensive Cancer Center
CCWFU # 99517

Appendix E – Adverse Event Log

WFBCCC Adverse Event (AE) Log

PI:

PID: _____

MRN: _____

Cycle Start Date:

Cycle End Date:

Cycle #: _____

*Serious Adverse Event: Hospitalization; Disability; Birth Defect; Life-threatening; Death.

CTCAE Version 4 - http://evs.nci.nih.gov/ftp1/CTCAE/CTCAE_4.03_2010-06-14_QuickReference_8.5x11.pdf

**THE USE OF LIPOSOMAL BUPIVACAINE FOR PAIN CONTROL FOLLOWING
MASTECTOMY AND BREAST RECONSTRUCTION**

Wake Forest Baptist Comprehensive Cancer Center
CCCWU # TBD

Appendix F – Pre-Operative Questionnaires

Revised Life Orientation Test (LOT-R)

Instructions:

Please answer the following questions about yourself by indicating the extent of your agreement using the following scale:

[0] = strongly disagree
[1] = disagree
[2] = neutral
[3] = agree
[4] = strongly agree

Be as honest as you can throughout, and try not to let your responses to one question influence your response to other questions. There are no right or wrong answers.

- 1 In uncertain times, I usually expect the best
- 2 It's easy for me to relax
- 3 If something can go wrong for me, it will
- 4 I'm always optimistic about my future
- 5 I enjoy my friends a lot
- 6 It's important for me to keep busy
- 7 I hardly ever expect things to go my way
- 8 I don't get upset too easily
- 9 I rarely count on good things happening to me
- 10 Overall, I expect more good things to happen to me than bad

Scoring:

1. Reverse code items 3, 7, and 9 prior to scoring (0=4) (1=3) (2=2) (3=1) (4=0).
2. Sum items 1, 3, 4, 7, 9, and 10 to obtain an overall score

Note Items 2, 5, 6, and 8 are filler items only. They are not scored as part of the revised scale.

The revised scale was constructed in order to eliminate two items from the original scale, which dealt more with coping style than with positive expectations for future outcomes. The correlation between the revised scale and the original scale is .95

Reference:

Scheier, M F, Carver C S, and Bridges, M W (1994). Distinguishing optimism from neuroticism (and trait anxiety, self-mastery, and self-esteem): A re-evaluation of the Life Orientation Test. *Journal of Personality and Social Psychology*, 67, 1063-1078

**THE USE OF LIPOSOMAL BUPIVACAINE FOR PAIN CONTROL FOLLOWING
MASTECTOMY AND BREAST RECONSTRUCTION**

Wake Forest Baptist Comprehensive Cancer Center
CCCWFU # TBD

PROMIS Item Bank v. 1.0 – Emotional Distress – Depression - Short Form 8b

Emotional Distress - Depression – Short Form 8b

Please respond to each item by marking one box per row.

In the past 7 days....		Never	Rarely	Sometimes	Often	Always
ED00P04	I felt worthless.....	 1	 2	 3	 4	 5
ED00P05	I felt that I had nothing to look forward to.....	 1	 2	 3	 4	 5
ED00P06	I felt helpless.....	 1	 2	 3	 4	 5
ED00P07	I felt sad.....	 1	 2	 3	 4	 5
ED00P08	I felt like a failure.....	 1	 2	 3	 4	 5
ED00P09	I felt depressed.....	 1	 2	 3	 4	 5
ED00P10	I felt unhappy.....	 1	 2	 3	 4	 5
ED00P11	I felt hopeless.....	 1	 2	 3	 4	 5

© 2008-2012 PROMIS Health Organization and PROMIS Cooperative Group

**THE USE OF LIPOSOMAL BUPIVACAINE FOR PAIN CONTROL FOLLOWING
MASTECTOMY AND BREAST RECONSTRUCTION**

Wake Forest Baptist Comprehensive Cancer Center
CCCWFU # TBD

PROMIS Item Bank v1.0 – Emotional Distress – Anxiety – Short Form 8a

Emotional Distress – Anxiety – Short Form 8a

Please respond to each question or statement by marking one box per row.

In the past 7 days...

		Never	Rarely	Sometimes	Often	Always
EDAN001 1	I felt fearful.....					
EDAN002 2	I found it hard to focus on anything other than my anxiety					
EDAN003 3	My worries overwhelmed me.....					
EDAN003 4	I felt uneasy					
EDAN006 5	I felt nervous.....					
EDAN007 6	I felt like I needed help for my anxiety					
EDAN008 7	I felt anxious.....					
EDAN009 8	I felt tense.....					

**THE USE OF LIPOSOMAL BUPIVACAINE FOR PAIN CONTROL FOLLOWING
MASTECTOMY AND BREAST RECONSTRUCTION**

Wake Forest Baptist Comprehensive Cancer Center
CCCWU # TBD

Instructions: Please reflect on past painful experiences and indicate the degree to which you experienced each of these thoughts and feelings when experiencing pain. The circle the appropriate number based on the scale below:

	Not at all	To a slight degree	To a moderate degree	To a great degree	All the time
1. I worry all the time about whether the pain will end	0	1	2	3	4
2. I feel I can't go on	0	1	2	3	4
3. It's terrible and I think it's never going to get any better	0	1	2	3	4
4. It's awful and I feel that it overwhelms me	0	1	2	3	4
5. I feel I can't stand it anymore	0	1	2	3	4
6. I become afraid that the pain will get worse	0	1	2	3	4
7. I keep thinking of other painful events	0	1	2	3	4
8. I anxiously want the pain to go away	0	1	2	3	4
9. I can't seem to keep it out of my mind	0	1	2	3	4
10. I keep thinking about how much it hurts	0	1	2	3	4
11. I keep thinking about how badly I want the pain to stop	0	1	2	3	4
12. There's nothing I can do to reduce the intensity of the pain	0	1	2	3	4
13. I wonder whether something serious may happen	0	1	2	3	4

cats

**THE USE OF LIPOSOMAL BUPIVACAINE FOR PAIN CONTROL FOLLOWING
MASTECTOMY AND BREAST RECONSTRUCTION**

Wake Forest Baptist Comprehensive Cancer Center
CCCWU # TBD

Appendix G – Pain Assessment

Subject Number: _____ DATE: ____/____/____ TIME: ____:____ AM/PM

1 - Rate the intensity of your worst pain in the past 24 hours related to your operated breast/chest.

0 1 2 3 4 5 6 7 8 9 10

2 – Please rate the intensity of breast pain that you have while eating.

0 1 2 3 4 5 6 7 8 9 10 Cannot Do

3 – If it has been one month or longer since your surgery please complete the following question:

Please lift your arms to the sides of your body at a 90-degree angle. Rate the intensity of breast pain that you have during this activity.

0 1 2 3 4 5 6 7 8 9 10 Cannot Do

Not Applicable

4 - Rate your level of disability in the past 24 hours to do normal daily activities.

0 1 2 3 4 5 6 7 8 9 10

5 - Rate your level of disability in the past 24 hours to do activities you enjoy.

0 1 2 3 4 5 6 7 8 9 10

6 - Did you take prescription pain pills in the past 24 hours? YES NO

If yes please circle the medication below and complete question 5b

THE USE OF LIPOSOMAL BUPIVACAINE FOR PAIN CONTROL FOLLOWING
MASTECTOMY AND BREAST RECONSTRUCTION

Wake Forest Baptist Comprehensive Cancer Center
CCCWU # TBD

6a1 – Oxycodone

6a2 - Hydromorphone (Dilaudid)

6a3 - Hydrocodone + acetaminophen (Vicodin, Norco)

6a4 Valium

6b - In the last 24 hours, how many prescription pills have you taken for your pain?

**THE USE OF LIPOSOMAL BUPIVACAINE FOR PAIN CONTROL FOLLOWING
MASTECTOMY AND BREAST RECONSTRUCTION**

Wake Forest Baptist Comprehensive Cancer Center
CCCWU # TBD

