5.2.2 Morphine equivalents used within the first month postoperatively

THE USE OF LIPOSOMAL BUPIVACAINE FOR PAIN CONTROL FOLLOWING MASTECTOMY AND IMMEDIATE IMPLANT BASED BREAST RECONSTRUCTION

Wake Forest Baptist Comprehensive Cancer Center
CCCWU # 99517

- 5.2.2.1 The number of doses of oral narcotics (hydrocodone-acetaminophen 1 tablet) for patients with immediate tissue expander reconstruction without other measure of pain control has been 4.2 at 24 hours and 4.0 at 48 hours¹⁷. This is approximately 3.3 morphine equivalents
- 5.2.2.2 We would expect the patients treated with liposomal bupivacaine to use an average of 2.5 intravenous morphine equivalents at the 48-hour point and decreased morphine equivalents in the liposomal bupivacaine over the first postoperative month.
- 5.2.3 Length of stay for hospitalization after mastectomy and breast reconstruction
 - 5.2.3.1 Length of stay for patients undergoing mastectomy and immediate reconstruction has been shown to be 41-47 hours on average²¹
 - 5.2.3.2 We believe liposomal bupivacaine will shorten this time to 36 hours±12 in the liposomal bupivacaine group, but not in the bupivacaine groups.
- 5.2.4 Readmission rates to the hospital within 2 months after mastectomy and breast reconstruction
 - 5.2.4.1 Patients who underwent tissue expander breast reconstruction have a readmission rate of approximately 4.34%²². We anticipate a readmission rate of approximately 2% Patients will be informed that if they are expected to undergo an axillary lymph node dissection at the time of surgery then they will be excluded from the study. Patients who are undergoing sentinel lymph node biopsies will be included in the study, but if their nodes are positive and there is an intraoperative decision to pursue axillary lymph node dissection they will subsequently be excluded from the study.
- 5.2.5 Frequency of postoperative opioid related adverse effects within the first week of surgery. This includes nausea, vomiting, pruritus, allergy, respiratory depression.
 - 5.2.5.1 After immediate breast reconstruction with implants, patients receiving bupivacaine had a 40% incidence of nausea and vomiting. Those not receiving a local anesthetic had a 75% incidence of nausea and vomiting¹⁷
 - 5.2.5.2 We predict a 30% incidence of opioid related adverse events in our liposomal bupivacaine group
- 5.2.6 Trajectory of postoperative recovery from pain within the first 2 months

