The study will be double blinded to both patients and providers including plastic and general surgeons involved in their operative care. We will enroll our patients in pharmacy randomization program, in which the pharmacy will deliver the appropriate medication per assigned group.

To monitor our primary outcomes, patients will be asked to rate their pain level on a visual analog scale (Table 2, Appendix Z) with activity every 12-hours after surgery during their post-procedure stay. The activity for which they will rate their pain will be the arm movements associated with eating. In the hospital, their visual analog scores will be provided to each patient in person by their nurse every 12 hours. Subject's pain scores will continue to be recorded every 12 hours via a phone call from a study team member for the first 48 hours after discharge. Additionally, while in the hospital, the amount of narcotics used will be recorded and converted into morphine equivalents.

Upon discharge, patients will be given a sheet to record their pain level and the amount of narcotics & benzodiazepines used (Appendix K). Both the amount of narcotics & benzodiazepines and the pain level are to be reported at the time of taking any narcotics & benzodiazepines. Patients will follow up with our clinic at 1 week, 3 weeks, and 5 weeks postoperatively. At week 1 patients will bring in their medication and pain diary, and fill out a pain assessment (Appendix G) in addition to a questionnaire assessing breast cancer surgery

THE USE OF LIPOSOMAL BUPIVACAINE FOR PAIN CONTROL FOLLOWING MASTECTOMY AND IMMEDIATE IMPLANT BASED BREAST RECONSTRUCTION

Wake Forest Baptist Comprehensive Cancer Center
CCCWU # 99517

disability (Appendix H)²³. During subsequent appointments made at 3 and 5 weeks postoperatively, they will be assessed and receive the pain assessment and breast cancer surgery disability assessments as well. When tissue expansion is initiated will be determined by the primary surgeon, but we will track the dates of the initiation of expansion as this will impact pain scores within the electronic medical record.

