Appendix J – Off-Study Form

Study Number: _____ PID: _____
Investigator: [name]. Date: ____ / ____ / ____

Name of Person Competing form

Did the subject meet eligibility criteria for study enrollment? Yes

Was the subject withdrawn from the study? Yes No

Reason(s) for withdrawal:

1. Patient exhibited progression of disease
2. Unacceptable toxicity

If Yes, Please specify whether the toxicity was:

II. Yes, Please specify whether the
 From Bupivacaine
 From Liposomal Bupivacaine
 From BOTH

**THE USE OF LIPOSOMAL BUPIVACAINE FOR PAIN CONTROL FOLLOWING
MASTECTOMY AND BREAST RECONSTRUCTION**

Wake Forest Baptist Comprehensive Cancer Center
CCCWFU # TBD

Other _____

3. Patient withdraw

If Yes, Please specify what portion of the study the subject wishes to withdraw from:

- For just the Drug A administration only
- For just the Drug B administration only
- For both
- For all components of the research study (including follow up in the medical record)

4. Investigator's discretion to withdraw patient from the study because continued participation in the study is not in the patient's best interest (*Describe below)

5. Undercurrent illness: a condition, injury, or disease unrelated to the intended disease for which the study is investigating, that renders continuing the treatment unsafe or regular follow-up impossible (*Describe below)

6. General or specific changes in the patient's condition that renders the patient ineligible for further investigational treatment (*Describe below)

7. Non-compliance with investigational treatment, protocol-required evaluations or follow-up visits (*Describe below)

8. Termination of the clinical trial by the clinical sponsor

Comment:

If reason for withdrawal includes #4, 5, 6, or 7 then please add comments clarifying this

information) _____

[figure not shown]
**THE USE OF LIPOSOMAL BUPIVACAINE FOR PAIN CONTROL FOLLOWING
MASTECTOMY AND BREAST RECONSTRUCTION**

Wake Forest Baptist Comprehensive Cancer Center
CCCWTFU # TBD

Appendix K- Pain Medication Diary. Assists patients in recording the amount and time of narcotic and benzodiazepine use.

Please use the scale below for reference when providing Pain Rating:

Visual Analogue Scale

	Date	Pain Medication Used (Include dose)	Number of pills taken	Time	Pain Rating (see scale above for reference)
1					
2					
3					
4					
5					
6					
7					
8					
9					
10					
11					
12					
13					
14					
15					

**THE USE OF LIPOSOMAL BUPIVACAINE FOR PAIN CONTROL FOLLOWING

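### Appendix G's pooled pill count cannot be converted to morphine equivalents, yet after week 1 it is the only scheduled patient report of intake for a first-month narcotic outcome

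*Combined protocol and SAP*

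**What the plan says.** The outcome in section 5.2.2 is "Morphine equivalents used within the first month postoperatively", matching objective 2.2.2. Section 10.2.2 compares the arms by t-test, after a log transformation if the data are not normal. It names no source form and no conversion rule.

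The plan describes three ways of recording intake:

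- **Hospital stay (6.1):** "while in the hospital, the amount of narcotics used will be recorded and converted into morphine equivalents".
- **After discharge (6.1, Appendix K):** "patients will be given a sheet to record their pain level and the amount of narcotics & benzodiazepines used (Appendix K"). Each diary line has a date, a time, a pill count and a field headed "Pain Medication Used (Include dose"). On return, 6.1 says: "At week 1 patients will bring in their medication and pain diary". The schedule in section 6.0 marks the diary at discharge and at one week only.
- **Clinic visits (6.1, Appendix G):** the form is completed at week 1 and again later: "During subsequent appointments made at 3 and 5 weeks postoperatively, they will be assessed and receive the pain assessment". Item 6 asks whether any prescribed pain tablets were taken in the previous 24 hours, then instructs: "If yes please circle the medication below and complete question 5b". The list names three opioids and Valium. The count item reads: "6b - In the last 24 hours, how many prescription pills have you taken for your pain". It is numbered 6b; there is no 5b.

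**The concern.** A morphine-equivalent dose needs the drug, the strength per pill and the number of pills for each opioid. Item 6b gives a single total across the circled drugs. Valium is a benzodiazepine with no morphine equivalent. Section 6.1 itself names benzodiazepines separately from narcotics, but Appendix G merges the two.

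This would matter little if a better instrument covered the whole outcome period. The diary is that instrument, but no return is stated after week 1, while the outcome runs to one month. For the later weeks the plan schedules only the form that cannot be converted. What that form omits cannot be recovered from a completed copy. At stake is whether the secondary outcome can be computed as defined.

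**Working it through.** No figure in the documents describes Appendix G. The nearest is the power statement in 10.2.2: effect size 0.6, 45 per group, two-sided alpha 0.05, 80% power. It reproduces: an exact two-sample t-test needs 44.6, so 45 per group, and has 80.4% power there. It does not depend on which form is used. (Section 10.3 plans 25 per arm, where power for 0.6 is 54.7%; that is a separate matter.)

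**Step 1: what the outcome needs.** For opioids j, morphine equivalents = sum over j of n_j × s_j × c_j, where n_j is pills taken, s_j strength per pill and c_j the conversion factor.

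**Step 2: what each form gives.**

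| Quantity | Appendix G, items 6/6b | Appendix K diary |
|---|---|---|
| Which drugs | Yes, circled | Yes, per line |
| Pills per drug | No; only N = sum of n_j + Valium pills | Yes |
| Strength or dose | No | Yes |
| Valium separable | No, if an opioid is also circled | Yes |
| Period covered | Previous 24 hours | Each intake after discharge |

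**Step 3: what can be recovered from 6b.**

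- One opioid circled, no Valium: n = N, so the dose follows if the strength is known from elsewhere.
- One opioid and Valium circled, N = 4, at least one of each taken: the opioid count is 1, 2 or 3, a threefold range before strength. A patient who took 2 oxycodone and 2 Valium reports 4, and reading that as opioid pills gives 4/2 = twice the true count.
- Two opioids circled, N = 4: the split can be 1+3, 2+2 or 3+1, so the dose is undetermined even if both strengths are known, unless the two pills are equivalent.

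These records are illustrations. The documents do not say how often several drugs are taken together.

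**Step 4: coverage.** The documents do not define a month in days, so take 28 to 31, with visits on their nominal days.

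- Days after the week-1 diary return: 28 − 7 = 21, to 31 − 7 = 24.
- Week 3 is day 21, inside the month. Week 5 is day 35, outside it.
- Share of the remaining days covered by the week-3 report: 1/24 = 4.2% to 1/21 = 4.8%.

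**Step 5: does a pooled count always dilute the effect?** This needs assumptions the documents do not supply. Suppose a mean of 4 opioid pills in the control arm, a true 25% reduction to 3, and Valium use unaffected by arm.

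- Relative reduction in the count with a mean of 1 Valium pill: (5 − 4)/5 = 20%. With 2: (6 − 5)/6 = 17%.
- The planned t-test depends on the standardised effect. In a simulation with patient-to-patient variation and equal potency, it moves from 0.32 to 0.31 (1 Valium pill) or 0.29 (2).
- With a fourfold potency spread unrelated to arm, the pill count has a standardised effect of 0.29 to 0.32, larger than the roughly 0.26 of the potency-weighted dose.

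The relative reduction therefore shrinks under these assumptions, but the sensitivity of the test can move either way.

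**The case against.** The strongest reply is that nothing in the documents makes Appendix G a source for this outcome. Section 6.1 calls it a pain assessment and names two other sources for narcotics: the hospital record, which is converted, and the Appendix K diary, which asks for drug and dose. Up to week 1 those sources allow opioids and Valium to be separated. A reader might infer that a 24-hour dose derived from 6b is wrong and that a true opioid-sparing effect is diluted. The documents do not support that: no such derivation is described, and dilution does not always follow (step 5).

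Nor can the plan's expectation of 3.3 falling to 2.5 morphine equivalents be used to size the effect. The 2.5 in 5.2.2.2 is in intravenous equivalents at 48 hours and does not carry over to a 24-hour pill count weeks later. The documents also give no figure for Valium's share of pills.

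All of that stands. It does not answer what happens after week 1. No later diary return is stated, the sources in 6.1 are not assigned to periods, and 10.2.2 is silent. The contents list calls Appendix G a daily diary, and section 9.0 sends a daily diary to REDCap without naming an appendix, so an analyst looking for later intake could reasonably turn to 6b.

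It is also fair to object that a better 6b alone is not enough. Snapshots of 24 hours cannot add up to first-month intake, so the fix has to cover the period as well as the form.

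**Conclusion.** The point holds in a limited form. Items 6/6b cannot yield morphine equivalents unless a patient took a single opioid of known strength. After week 1 they are the only scheduled patient report of intake, and only the week-3 report falls inside the month, covering about 4% to 5% of the remaining days. As written, the first-month outcome has no usable scheduled source beyond week 1.

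This rests on reading the stated week-1 return as the end of diary collection, on nominal visit days, and on a month of 28 to 31 days. The size and direction of any bias between arms cannot be worked out from the documents. The point concerns a secondary outcome and does not touch the primary pain outcome.

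**What to change.** 1. **Appendix G.** Replace 6b with one line per listed drug, giving strength per pill and number of pills in the past 24 hours. Put Valium on its own line. Correct the pointer from 5b to 6b.
2. **Section 10.2.2, conversion.** State that only the opioid lines are converted to morphine equivalents.
3. **Section 10.2.2, source by period.** Name the hospital record to discharge and Appendix K to week 1. After that, choose one: continue Appendix K to one month, or restate the outcome after week 1 as 24-hour morphine equivalents at the visit.

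The cost is a form and REDCap change, a few sentences in 10.2.2 and a few more boxes for the patient, with no extra visit or staff. Continuing the diary would ask the patient for about three more weeks of entries; it could be collected at the existing week-3 and week-5 visits. Restating the outcome avoids that burden but gives up cumulative first-month intake.

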Appendix H - Disability Assessment

For the following, indicate whether pain since your surgery has affected your ability to perform these activities:

Subject Number: _____ DATE: ____/____/____ TIME: ____:____AM/PM

6a: Carry or lift children

- 1 - Not relevant, I don't do this
- 2 - I can do this without any problem
- 3 - I can do this but with difficulties due to pain
- 4 - I can't do this due to pain from my surgery

6b: Carrying grocery bags, luggage, or heavy bags

- 1 - Not relevant, I don't do this
- 2 - I can do this without any problem
- 3 - I can do this but with difficulties due to pain
- 4 - I can't do this due to pain from my surgery

6c: Do Laundry

- 1 - Not relevant, I don't do this
- 2 - I can do this without any problem
- 3 - I can do this but with difficulties due to pain
- 4 - I can't do this due to pain from my surgery

6d: Kitchen chores, cooking

- 1 - Not relevant, I don't do this
- 2 - I can do this without any problem
- 3 - I can do this but with difficulties due to pain
- 4 - I can't do this due to pain from my surgery

6e: Opening a heavy door

- 1 - Not relevant, I don't do this
- 2 - I can do this without any problem
- 3 - I can do this but with difficulties due to pain
- 4 - I can't do this due to pain from my surgery

6f: Put on a brassiere

- 1 - Not relevant, I don't do this
- 2 - I can do this without any problem
- 3 - I can do this but with difficulties due to pain
- 4 - I can't do this due to pain from my surgery

6g: Put on a coat

- 1 - Not relevant, I don't do this
- 2 - I can do this without any problem
- 3 - I can do this but with difficulties due to pain
- 4 - I can't do this due to pain from my surgery

6h: Reaching high shelves, over your head

- 1 - Not relevant, I don't do this
- 2 - I can do this without any problem
- 3 - I can do this but with difficulties due to pain
- 4 - I can't do this due to pain from my surgery

6i: Sleep

- 1 - Not relevant, I don't do this
- 2 - I can do this without any problem
- 3 - I can do this but with difficulties due to pain
- 4 - I can't do this due to pain from my surgery

**THE USE OF LIPOSOMAL BUPIVACAINE FOR PAIN CONTROL FOLLOWING
MASTECTOMY AND BREAST RECONSTRUCTION**

Wake Forest Baptist Comprehensive Cancer Center

CCCFU # TBD

6j: Take a sweater on or off

- 1 - Not relevant, I don't do this
- 2 - I can do this without any problem
- 3 - I can do this but with difficulties due to pain
- 4 - I can't do this due to pain from my surgery

6k: Vacuuming or washing floors

- 1 - Not relevant, I don't do this
- 2 - I can do this without any problem
- 3 - I can do this but with difficulties due to pain
- 4 - I can't do this due to pain from my surgery

6l: Washing hair / neck

[figure not shown]
- 1 - Not relevant, I don't do this
- 2 - I can do this without any problem
- 3 - I can do this but with difficulties due to pain
- 4 - I can't do this due to pain from my surgery

THE USE OF LIPOSOMAL BUPIVACAINE FOR PAIN CONTROL FOLLOWING MASTECTOMY AND BREAST RECONSTRUCTION

Wake Forest Baptist Comprehensive Cancer Center
CCCWFU # TBD

